**D.11.5.1. Hypothesis 2a: Sleep BP on HBPM will provide an accurate estimate of sleep BP on ABPM.**

We will assemble a scatterplot of mean sleep SBP on HBPM versus ABPM and a intraclass correlation coefficient will be calculated. The statistical significance of the difference in mean sleep SBP on HBPM versus ABPM will be calculated using paired t-tests. The analysis will be repeated using sleep DBP on HBPM versus ABPM. We will create Bland-Altman plots showing the difference between sleep BP on HBPM versus ABPM by ABPM sleep BP level. We will calculate the percentage of participants who have a 10 mm Hg or larger absolute difference in their mean sleep SBP or a 5 mm Hg or larger absolute difference in their mean sleep DBP when measured by HBPM versus ABPM. Differences in mean sleep BP (SBP and DBP, separately) measured on HBPM versus ABPM will be calculated within age, race/ethnicity and sex sub-groupings. We will calculate the overall agreement and Kappa statistic between nocturnal hypertension on HBPM and ABPM, and test for a difference in prevalence using McNemar's test. We will compare differences in mean sleep SBP and DBP by randomization assignment using t-tests. If differences are statistically significant, analyses will include adjustment for randomization assignment.

**D.11.5.2. Hypothesis 2b: HBPM will be better tolerated than ABPM.** An overall score on the HBPM/ABPM tolerability questionnaire will be calculated by summing the scores on the eight Likert-type items after reverse coding positively-framed items (i.e., those with higher scores indicating better tolerability). Consistent with the approach of Viera, poor tolerance will be defined as an overall score  $\geq 75^{\text{th}}$  percentile on the results for ABPM. The cut-point identified for ABPM will be applied to define poor HBPM tolerability. Also, the percent of participants who report "pain", "skin irritation" and "bruising" from the ABPM device, and separately, the HBPM device will be calculated. The statistical significance of differences in responses to these items when wearing the HBPM and ABPM devices will be calculated using McNemar tests.

**D.11.6. Aim 3. Compare the associations of unattended versus attended clinic BP, unattended clinic BP versus awake BP on ABPM, and sleep BP on HBPM versus ABPM with two markers of end-organ damage, LVMI and ACR.**

**Hypothesis 3a:** The association with end-organ damage will be stronger for unattended vs. attended clinic BP.

**Hypothesis 3b:** The association with end-organ damage will be similar for unattended clinic and awake BP.

**Hypothesis 3c:** The association with end-organ damage will be similar for sleep BP by HBPM and ABPM.

Below we describe the analysis plan for testing Hypothesis 3a. The analysis plan will be identical for Hypotheses 3b and 3c. We will calculate the intraclass correlation coefficients between (1) attended clinic BP and (2) unattended clinic BP with LVMI. The statistical significance of the difference in the correlation coefficients will be calculated using the Fisher r-to-z transformation accounting for the within-person correlation between unattended and attended BP measurements. Also, the association between clinic BP, measured unattended and attended, separately, and LVMI will be calculated using linear regression. For these models, clinic BP will be modeled in categories, using restricted quadratic splines, and, if appropriate, as a continuous variable (e.g., per 10 mm Hg higher SBP). Two levels of adjustment will be performed as described in **Section D.11.2.**

For secondary testing of Hypothesis 3, we will model the outcome of LVH defined as an  $\text{LVMI} \geq 96 \text{ g/m}^2$  in women and  $\text{LVMI} \geq 116 \text{ g/m}^2$  in men using Poisson regression with robust standard errors and two levels of adjustment (**Section D.11.2**). The analyses will be repeated for the outcome of the ACR. When modeled as a continuous variable, ACR will be log-transformed due to its skewed distribution. As a dichotomous variable, albuminuria will be defined as an sex/race-adjusted  $\text{ACR} > 25 \text{ mg/g}$ .

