Unattended: SBP/DBP readings  $\geq$ 135 or 85 mm Hg

**Table 4.** Agreement between hypertension on ABPM and clinic BP, N=569

		ABPM and unattended clinic BP in hypertensive range		N (%)
		Yes, %	No, %	
ABPM and attended clinic BP in hypertensive range	Yes, %	25 (4.4)	1 (0.2)	26 (4.6)
	No, %	14 (2.5)	529 (93.0)	543 (95.4)
	N (%)	39 (6.9)	530 (93.2)	569 (100)
Kappa: 0.76				

**Table 5.** Agreement between white coat hypertension on ABPM and clinic BP, N

		Hypertensive unattended clinic BP with normal ABPM		
		Yes, %	No, %	N (%)
Hypertensive attended clinic BP with normal ABPM	Yes, %	15 (2.6)	0 (0.0)	15 (2.6)
	No, %	26 (4.6)	528 (92.8)	554 (97.4)
N (%)		41(7.2)	528 (92.8)	569 (100)

Kappa: 0.52

**Table 6.** Agreement between masked hypertension on ABPM and clinic BP, N

		Hypertensive ABPM with normal unattended clinic BP		
		Yes, %	No, %	N (%)
Hypertensive ABPM with normal attended clinic BP	Yes, %	17 (3.0)	14 (2.5)	31 (5.5)
	No, %	1 (0.2)	537 (94.4)	538 (94.6)
N (%)		18 (3.2)	551 (96.8)	569 (100)
Kappa: 0.68				

**Table 7.** The difference between sleep BP on HBPM versus sleep BP on ABPM, N = 547

	ABPM Mean (SD) Median, (min – max)	HBPM Mean (SD) Median (min – max)	Mean difference, (95% CI)	P (difference = 0)
Sleep systolic BP	104.1 (10.5) 103.3 (72.3 - 145.0)	106.4 (11.5) 106.0 (74.0 - 159.0)	-2.3 (-3.0, -1.5)	<.0001
Sleep diastolic BP	60.4 (7.5) 59.8 (42.1 - 95.4)	62.3 (8.3) 62.0 (38.0 - 88.0)	-1.9 (-2.5,-1.4)	<.0001

**Table 8.** Side effects and tolerability of HBPM versus ABPM, N = 603.

	Occurred with ABPM only, N (%)	Occurred with HBPM only, N (%)	Occurred with both ABPM and HBPM, N (%)	Didn't occur for ABPM or HBPM, N (%)
Side effects				
Pain while wearing the monitor	160 (26.5)	37 (6.1)	128 (21.2)	278 (46.1)
Irritation while wearing the monitor	178 (29.5)	26 (4.3)	232 (38.5)	167 (27.7)
Bruising while wearing the monitor	84 (13.9)	19 (3.2)	54 (9.0)	446 (74.0)
Tolerability				
Monitor was heavy to wear	133 (22.1)	57 (9.5)	139 (23.1)	274 (45.4)
Monitor was uncomfortable to wear	109 (18.1)	68 (11.3)	399 (66.2)	27 (4.5)
Monitor was straightforward to use	12 (2.0)	6 (1.0)	578 (95.9)	7 (1.2)
Monitor was cumbersome or awkward to wear	130 (21.6)	27 (4.5)	377 (62.5)	69 (11.4)
Noise of the monitor was disturbing to me	91 (15.1)	71 (11.8)	102 (16.9)	339 (56.2)
Noise of the monitor disturb others	67 (11.1)	24 (4.0)	43 (7.1)	469 (77.8)
Monitor was embarrassing to wear	212 (35.2)	10 (1.7)	93 (15.4)	288 (47.8)

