**D.11.3. Exploratory statistics comparing unattended and attended BP.** We will calculate characteristics of participants by randomization assignment: unattended then attended clinic BP measurement or attended then unattended clinic BP measurement at the first visit. Scatterplots will be assembled to show the relationship between unattended clinic BP versus awake BP and attended clinic BP versus awake BP. For each comparison, intraclass correlation coefficients will be calculated. The statistical significance of the difference in the correlation coefficients will be calculated using the Fisher r-to-z transformation accounting for the correlation between attended and unattended clinic BP. We will also assemble Bland-Altman plots showing the differences between unattended and attended BP, separately, versus awake BP on ABPM.

**D.11.4. Aim 1. Test whether measuring unattended clinic BP with an automated device will provide a more accurate estimate of awake BP on ABPM than measuring attended clinic BP with an automated device.** Our primary analyses for Hypothesis 1 will be tested using the first three clinic BP measurements obtained at Visits 1 and 2. In sensitivity analyses, we will use the fourth through sixth BP measurements from these visits. Separate analyses will be performed for SBP and DBP.

**D.11.4.1. Hypothesis 1a: The absolute difference with awake BP will be smaller for unattended vs. attended clinic BP.** The absolute difference between mean unattended clinic BP and awake BP and mean attended clinic BP and awake BP, separately, will be calculated. We will test whether these differences are statistically significantly different from zero using paired t-tests. Next, we will determine whether the absolute difference between unattended clinic BP and awake BP is smaller than the absolute difference between attended clinic BP and awake BP by calculating if the difference in differences (i.e., absolute difference between unattended clinic BP and awake BP minus the absolute difference between attended clinic BP and awake BP) is less than zero using a paired t-test. If the absolute differences between unattended and attended clinic BP and awake BP differs by randomization assignment, we will use a mixed model with randomization assignment as a covariate. This analysis will be performed in the overall population and in sub-groups defined by age (categorized in tertiles), race/ethnicity (white, African American, Hispanic) and sex.

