**D.12.2.1. Minimum detectable effect size - hypothesis 2a.** We assumed a standard deviation of sleep SBP of 15 mm Hg and sleep DBP of 10 mm Hg when measured using ABPM and HBPM. Also, the correlation between sleep BP on ABPM and HBPM was assumed to be 0.5 for SBP and DBP. For this analysis, we are testing that mean sleep BP is equivalent when measured by HBPM and ABPM. A sample size of 600 participants will provide 80% statistical power to exclude an absolute mean difference equal to or larger than 2.1 mmHg for SBP or 1.4 mmHg for DBP comparing ABPM versus HBPM exists. In a sub-group of 160 participants, we can exclude an absolute mean difference equal to or larger than 4.0 mmHg for SBP or 2.7 mmHg for DBP. If the correlation of sleep BP on ABPM and HBPM is higher (e.g., 0.7 or 0.9), we can exclude smaller absolute differences. A sample size of 600 participants will provide narrow confidence intervals for the observed agreement and kappa statistic for nocturnal hypertension comparing HBPM and ABPM. For example, the 95% confidence interval for an observed agreement of 80% and 90% would be 77%-83% and 88%-92%, respectively, and for a kappa statistic of 0.6 and 0.8 would be 0.54-0.66 and 0.75-0.85, respectively.

**D.12.2.2. Minimum detectable effect size - hypothesis 2b.** By definition, 25% of participants will have poor tolerance to ABPM. The minimum detectable difference in the prevalence of poor tolerance comparing HBPM versus ABPM depends on the percentage of participants who have poor tolerance to one method but not to the other. With a sample size of 600 participants, we can detect a difference in poor tolerance of ABPM and HBPM of 3% (25% versus 22%) if 20% of participants report poor tolerance to both methods (e.g., if 5% has poor tolerance to ABPM but not to HBPM, and 2% has poor tolerance to HBPM but not to ABPM). Assuming 5% of participants experience bruising with both ABPM and HBPM, we will have 80% power to detect a difference in the prevalence of bruising of 3% or larger comparing ABPM and HBPM.

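### D.11.5.1 plots the HBPM-minus-ABPM sleep BP difference against ABPM itself, which builds in a downward trend even when neither device's error depends on BP level

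*Combined protocol and SAP*

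**What the plan says.** Section D.11.5.1 sets out how Hypothesis 2a, that sleep BP on HBPM accurately estimates sleep BP on ABPM, will be examined. Besides a scatterplot, an intraclass correlation, a paired t-test, the percentage of participants beyond 10 mm Hg (systolic) or 5 mm Hg (diastolic), and agreement on nocturnal hypertension, it states: "We will create Bland-Altman plots showing the difference between sleep BP on HBPM versus ABPM by ABPM sleep BP level". The section does not mention the mean of the two methods, limits of agreement, or regression to the mean for this plot.

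Three design features bear on the axis:

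- The two devices are worn in sequence, in randomized order, on different nights (D.6.3, D.7).
- A complete ABPM recording may contain as few as 5 sleep readings, and a complete HBPM recording contains three (D.10.4).
- For planning, D.12.2.1 says "We assumed a standard deviation of sleep SBP of 15 mm Hg and sleep DBP of 10 mm Hg when measured using ABPM and HBPM", and that "the correlation between sleep BP on ABPM and HBPM was assumed to be 0.5 for SBP and DBP".

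**The concern.** The difference HBPM - ABPM contains ABPM with a minus sign. A participant whose ABPM night happened to read low is placed to the left of the plot, and the same error pushes that participant's difference up. A high ABPM night does the opposite. The result is a downward slope that comes from error in ABPM and not from any dependence of HBPM's error on BP level.

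This display is meant to show whether disagreement changes with BP level. On the planned axis, a reader would be led to conclude that HBPM over-reads at low sleep BP and under-reads at high sleep BP. From that it is a short step to thinking that HBPM misses nocturnal hypertension. Two devices with no level-dependent error would give the same picture.

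**Working it through.** **Notation.** A = ABPM sleep mean and H = HBPM sleep mean, with SDs sA and sH and correlation r. D = H - A.

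- Slope of D on A = Cov(H - A, A)/Var(A) = r·sH/sA - 1. With equal SDs this is r - 1.
- Slope of D on the mean M = (A + H)/2 is 2(sH² - sA²)/(sH² + sA² + 2·r·sA·sH). With equal SDs this is 0.

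The plan states no slope, so there is no figure of its own to reproduce.

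**Step 1: planning inputs (D.12.2.1).** sA = sH = 15 (systolic) or 10 (diastolic), r = 0.5.

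- On A: 0.5 - 1 = -0.50 for both.
- On the mean: 0.00 for both.
- A simulation of one million pairs with equal noise and no level-dependent error gave -0.500 and 0.000.

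**Step 2: reported sleep BP (Analysis Plan, Table 7, N = 547).** The inputs are:

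| | ABPM mean (SD) | HBPM mean (SD) | ABPM - HBPM (95% CI) |
|---|---|---|---|
| Systolic | 104.1 (10.5) | 106.4 (11.5) | -2.3 (-3.0, -1.5) |
| Diastolic | 60.4 (7.5) | 62.3 (8.3) | -1.9 (-2.5, -1.4) |

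The differences agree with the means: 104.1 - 106.4 = -2.3 and 60.4 - 62.3 = -1.9. The table does not give r, so it is recovered from the paired interval:

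- SD of D = half-width × √547 / 1.964. Systolic: 0.75 × 23.39/1.964 = 8.93. Diastolic: 0.55 × 23.39/1.964 = 6.55.
- r = (sA² + sH² - SD²)/(2·sA·sH). Systolic: (110.25 + 132.25 - 79.74)/241.5 = 0.67. Diastolic: (56.25 + 68.89 - 42.88)/124.5 = 0.66.
- Slope on A. Systolic: 0.674 × 11.5/10.5 - 1 = -0.26 (rounding range -0.32 to -0.21). Diastolic: 0.661 × 8.3/7.5 - 1 = -0.27 (-0.35 to -0.19).
- Slope on the mean. Systolic: 44/405.3 = +0.11 (+0.10 to +0.12). Diastolic: 25.28/207.4 = +0.12 (+0.10 to +0.14).

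On the planned axis the fitted systolic difference runs from 2.3 + 0.262 × 21 = +7.8 mm Hg at 2 SD below the ABPM mean to 2.3 - 0.262 × 21 = -3.2 mm Hg at 2 SD above it.

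**Step 3: can this arise with no level-dependent bias?** Let A and H be the same true value, plus a constant shift for H, plus independent noise. The systolic figures then give:

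- Variance of the true value = r·sA·sH = 162.76/2 = 81.4.
- Noise variance of A = 110.25 - 81.4 = 28.9; of H = 132.25 - 81.4 = 50.9.
- Slope of D on A = -28.9/110.25 = -0.26.
- Slope of D on the mean = [(50.9 - 28.9)/2]/(405.3/4) = 11.0/101.3 = +0.11.

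A model with a constant shift and nothing else reproduces both slopes.

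**Step 4: is the noise gap plausible?** HBPM takes three readings. ABPM reads every 30 minutes, or about 14 times over the 7-hour night used as an example in the manual. If readings are independent with within-night SD w, the variance gap is w²(1/3 - 1/14) = 22, so w is about 9 mm Hg. The documents do not give w. For 12 to 20 ABPM readings it would need to be 8.8 to 9.4.

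**The case against.** **ABPM is the reference standard.** The documents name it so, and Hypothesis 2a asks how well HBPM estimates the ABPM value. Plotting the difference by reference level answers a legitimate question: what HBPM is expected to read, given an observed one-night ABPM value. That stands as a description. It does not make the slope a measure of device bias, because that would require an ABPM sleep mean without error. A mean that may rest on 5 readings, from a different night, does not meet that condition, and the plan itself assumes a correlation of only 0.5.

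**Nothing is inferred from the plot.** This is largely right. D.11.5.1 plans no regression or trend test on it. The paired t-test, intraclass correlation, kappa, McNemar test and 10/5 mm Hg percentages do not depend on the axis. The point concerns how a figure will be read.

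**The sources differ.** The plot is specified in the D sections, which name other devices than the manual, while Table 7 reports results. The -0.50 needs only the D sections; Table 7 serves to show the size in the reported data.

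**Does D.11.3 do the same for clinic BP?** A reader might infer so from "We will also assemble Bland-Altman plots showing the differences between unattended and attended BP, separately, versus awake BP on ABPM". The sentence does not support that reading. Awake ABPM can be the comparator within the difference, and no horizontal axis is stated.

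**Conclusion.** The point holds for D.11.5.1. The planned axis builds in a downward slope for HBPM - ABPM of -0.50 on the planning inputs, and about -0.26 (systolic) and -0.27 (diastolic) on the Analysis Plan's Table 7. If the subtraction is done the other way, as in Table 7, the built-in trend is upward. The conclusion rests on ABPM sleep BP having measurement error, which the design supports.

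A reader who compares -0.26 with +0.11 might infer that the planned axis reverses the sign of a true upward trend. The documents do not support that. Step 3 shows that both slopes arise with no level-dependent bias once HBPM is the noisier method, and the planning inputs give zero on the mean axis, not a reversal. The +0.11 is not evidence of proportional bias.

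Nor is the absence of these plots from the Analysis Plan's list of tables part of this point; that is missing detail only. The change is worth making, but it concerns a descriptive figure and leaves every planned test and the sample size as they are.

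**What to change.** In D.11.5.1, replace the closing phrase of the plot sentence, which puts the ABPM sleep value on the axis, with: by the mean of the HBPM and ABPM sleep BP. Report the bias and the limits of agreement, for systolic and diastolic BP separately.

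If a slope on the mean is shown, add one sentence of caution: three HBPM readings against a larger number of ABPM sleep readings give unequal error variance, which can itself produce a small positive slope, so the slope is not proof of proportional bias.

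The cost is one phrase and one or two sentences. No new data are needed.

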#### **Statistical analysis:**

1. Calculate the distribution of the variables in **Table 1**, overall, and separately for participants who were attended then unattended, unattended then attended, as well as participants who underwent ABPM before HBPM, and HBPM before ABPM.
2. Do the following analysis for **Table 2** for those with complete BP data on ABPM, attended, and unattended:
  - a. For awake systolic BP, calculate the mean (with standard deviation) BP on ABPM, attended, and unattended
  - b. Calculate the absolute mean difference with 95% confidence intervals for ABPM vs. attended, ABPM vs. unattended, and attended vs. unattended, using mixed model to determine the difference between the differences.
  - c. Repeat items **2a** and **2b** for awake diastolic BP on ABPM, attended and unattended.

3. Do the following analysis for **Table 3** for those with complete BP data on ABPM, attended, and unattended:
  - a. Calculate the percentage (with 95% confidence interval) of participants with hypertension on awake ABPM (i.e., ABPM\_HYPER = 1)
  - b. Calculate the percentage (with 95% confidence interval) of participants with hypertension on attended BP measurements (i.e., ATTENDED\_HYPER = 1).
  - c. Calculate the percentage (with 95% confidence interval) of participants with hypertension on unattended BP measurements (i.e., UNATTENDED\_HYPER = 1).
  - d. Calculate the percentage (with 95% confidence intervals) of participants with hypertension on attended and awake ABPM (i.e., HYP\_AB\_ATTEND = 1).
  - e. Calculate the percentage (with 95% confidence intervals) of participants with hypertension on unattended and awake ABPM (i.e., HYP\_AB\_UNATTEND = 1).
  - f. Calculate the percentage (with 95% confidence intervals) of participants with white coat hypertension on ABPM and attended BP (i.e., WHIT\_AB\_ATTEND = 1).
  - g. Calculate the percentage (with 95% confidence intervals) of participants with white coat hypertension on ABPM and unattended BP (i.e., WHIT\_AB\_UNATTEND = 1)
  - h. Calculate the percentage (with 95% confidence intervals) of participants with masked hypertension on ABPM and attended BP (i.e., MASK\_AB\_ATTEND = 1).
  - i. Calculate the percentage (with 95% confidence intervals) of participants with masked hypertension on ABPM and unattended BP (i.e., MASK\_AB\_UNATTEND = 1)
4. Do the following analysis for those with complete BP data on ABPM, attended, and unattended:

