  - a. **Table 4**, use a 2 x 2 table to determine the agreement hypertension on ABPM and clinic BP (i.e., HYP\_AB\_ATTEND versus HYP\_AB\_UNATTEND); provide the p-value from kappa statistics.
  - b. **Table 5**, use a 2 x 2 table to determine the agreement white coat hypertension on ABPM and clinic BP (i.e., WHIT\_AB\_ATTEND versus WHIT\_AB\_UNATTEND); provide the p-value from kappa statistics.
  - c. **Table 6**, use a 2 x 2 table to determine the agreement masked hypertension on ABPM and clinic BP (i.e., WHIT\_AB\_ATTEND versus WHIT\_AB\_UNATTEND); provide the p-value from kappa statistics.
5. Do the following analysis for **Table 7** for those with complete sleep BP data on ABPM and HBPM:
  - a. For sleep systolic BP, calculate the mean BP (with standard deviation) on ABPM and HBPM.
  - b. Calculate the absolute mean difference with 95% confidence intervals for ABPM vs. HBPM, using a paired T-test.
  - c. Repeat items 5a and 5b for sleep diastolic BP on ABPM and HBPM.
6. **Table 8**. Calculate the number and percentage of side effects and tolerability (**listed in Table 8**) that occurred in ABPM only, HBPM only, both ABPM and HBPM, and occurred for neither ABPM nor HBPM.
7. **Table 9**. Restrict the analysis to those with complete data on attended and unattended BP and complete data on left ventricular mass index .
  - a. Use linear regression to determine the relationship between attended SBP with left ventricular mass index.
  - b. Repeat the analysis for attended DBP, unattended SBP, unattended DBP with left ventricular mass index, separately.

8. **Table 10.** Restrict the analysis to those with complete BP data on unattended and awake ABPM and complete data on left ventricular mass index.
  - a. Use linear regression to determine the relationship between unattended SBP with left ventricular mass index.
  - b. Repeat the analysis for unattended DBP, awake SBP on ABPM, awake DBP on ABPM with left ventricular mass index, separately.
9. **Table 11.** Restrict the analysis to those with complete sleep BP data on ABPM and HBPM and complete data on left ventricular mass index.
  - c. Use linear regression to determine the relationship between sleep SBP on ABPM with left ventricular mass index.
  - d. Repeat the analysis for sleep DBP on ABPM, sleep SBP on HBPM, and sleep DBP on HBPM with left ventricular mass index, separately.

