10. **Table 12.** Restrict the analysis to those with complete data on attended and unattended BP and complete data on urinary albumin-to-creatinine ratio.
  - c. Use linear regression to determine the relationship between attended SBP with urinary albumin-to-creatinine ratio.
  - d. Repeat the analysis for attended DBP, unattended SBP, unattended DBP with urinary albumin-to-creatinine ratio, separately.
11. **Table 13.** Restrict the analysis to those with complete BP data on unattended and awake ABPM and complete data on urinary albumin-to-creatinine ratio.
  - e. Use linear regression to determine the relationship between unattended SBP with urinary albumin-to-creatinine ratio.
  - f. Repeat the analysis for unattended DBP, awake SBP on ABPM, awake DBP on ABPM with urinary albumin-to-creatinine ratio, separately.
12. **Table 14.** Restrict the analysis to those with complete sleep BP data on ABPM and HBPM and complete data on urinary albumin-to-creatinine ratio.
  - g. Use linear regression to determine the relationship between sleep SBP on ABPM with urinary albumin-to-creatinine ratio.
  - h. Repeat the analysis for sleep DBP on ABPM, sleep SBP on HBPM, and sleep DBP on HBPM with urinary albumin-to-creatinine ratio, separately.

Table 1. Characteristics of Better BP participants by randomization.

	Overall N = 603	Attended then unattended, N = 301	Unattended then attended, N = 302	ABPM then HBPM, N = 302	HBPM then ABPM, N = 301
Age, yrs,					
Mean (SD)	38.6 (15.1)	39.4 (16.0)	37.9 (14.1)	39.2 (15.7)	38.1 (14.5)
Median (min – max)	34.0 (18.0 - 83.0)	35.0 (19.0 - 83.0)	34.0 (18.0 - 83.0)	35.5 (18.0 - 79.0)	33.0 (19.0 - 83.0)
Women, %	382 (63.3)	190 (63.1)	192 (63.6)	191 (63.2)	191 (63.5)
Race, %					
Hispanic	39 (6.5)	24 (8.0)	15 (5.0)	22 (7.3)	17 (5.6)
Non-Hispanic, Asian	90 (14.9)	39 (13.0)	51 (16.9)	47 (15.6)	43 (14.3)
Non-Hispanic, Black	132 (21.9)	64 (21.3)	68 (22.5)	61 (20.2)	71 (23.6)
Non-Hispanic, White	291 (48.3)	150 (49.8)	141 (46.7)	148 (49.0)	143 (47.5)
Other non-Hispanic race/ethnicity	51 (8.5)	24 (8.0)	27 (8.9)	24 (7.9)	27 (9.0)
Body Mass Index					
Mean (SD)	27.2 (5.9)	26.8 (5.9)	27.5 (5.8)	27.2 (5.6)	27.2 (6.1)
Median (min – max)	25.9 (13.0 - 55.5)	25.6 (13.0 - 55.5)	26.5 (17.2 - 53.0)	26.0 (13.0 - 53.0)	25.9 (17.3 - 55.5)
Attended office blood pressure					
Systolic BP					
Mean (SD)	119.4 (12.0)	118.9 (12.1)	120.0 (12.0)	119.7 (11.9)	119.2 (12.2)

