**Table 3. Limitations of prior studies comparing sleep BP on HBPM versus ABPM**

1. The order of home monitoring and ABPM to assess sleep BP was not randomized. In prior studies, patients chose the order in which they completed home monitoring and ABPM to assess sleep BP.
2. Studies did not include US populations. Sleep BP and nocturnal hypertension have not been compared between HBPM and ABPM in African Americans, a population with a high prevalence of nocturnal hypertension.
3. Over 80% of patients were taking antihypertensive medication. Prior studies have primarily included people taking antihypertensive medication, with some people taking medication before bedtime. The role of home monitoring to assess sleep BP has not been evaluated among people not taking antihypertensive medication.
4. The agreement of nocturnal hypertension defined using HBPM versus ABPM was not reported. Prior studies have only reported the correlation and mean difference in sleep BP levels on HBPM and ABPM.
5. The tolerability of assessing sleep BP on HBPM was not assessed. Sleep HBPM may be better tolerated than ABPM.

**C. INNOVATION.** The proposed study has several innovative features:

- We will enroll patients with a wide range of clinic BP and who are not taking antihypertensive medication. The study examines unattended clinic BP measurement for the diagnosis of hypertension.
- The study will use a within-subjects randomized design which will control for order effects and regression to the mean. Participants will be randomized to have their BP measured in the clinic attended or unattended in counterbalanced order (i.e. attended followed by unattended or vice versa). Additionally, participants will be randomized to have their sleep BP measured first by ABPM then by HBPM or vice-versa. *The lack of randomized controlled data on BP measured unattended versus attended has resulted in a low grade of evidence (Grade D) in the Canadian hypertension guideline.*
- *The study will compare unattended clinic BP versus attended clinic BP using the same oscillometric device. In prior studies, attended clinic BP was measured by auscultation. The use of oscillometric BP devices is becoming more widespread in clinical practice as mercury sphygmomanometers have environmental concerns and the need for frequent calibration of aneroid devices is recognized as a major problem.*

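### Aim 2: adjustment for device order hangs on a significance pre-test, and the SAP's paired t-test omits order, although Table 1 puts the HBPM minus ABPM sleep SBP difference near 1.0 mm Hg in one order and 3.5 in the other

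*Combined protocol and SAP*

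**What the plan says.** Protocol section C presents randomised order as a reason for the design: "The study will use a within-subjects randomized design which will control for order effects and regression to the mean". D.7 randomises device order (ABPM then HBPM, or the reverse) separately at each site.

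For Hypothesis 2a, D.11.5.1 plans a paired t-test of mean sleep BP on the two devices. It then adds "We will compare differences in mean sleep SBP and DBP by randomization assignment using t-tests", and after that: "If differences are statistically significant, analyses will include adjustment for randomization assignment".

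The SAP's instruction for the same comparison (Statistical analysis, item 5b) is: "Calculate the absolute mean difference with 95% confidence intervals for ABPM vs. HBPM, using a paired T-test". Item 5 has no test by order, no order or period term and no result by order, and Table 7 has the same layout. SAP item 1 does use device order, but only to describe participants in Table 1.

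**The concern.** There are two problems. First, D.11.5.1 lets a significance test on the trial data choose the model. Order is randomised and recorded for everyone, so nothing is gained by leaving its inclusion to a test. Second, the SAP carries over neither the test nor the adjustment, so the two documents do not describe the same analysis.

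This matters because Aim 2 asks how far one night of HBPM departs from ABPM. If the departure depends on which device was worn first, a single pooled difference does not tell the reader so. The paired t-test also leaves the order effect in the residual variation.

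**Working it through.** **Inputs.** SAP Table 1, asleep BP by device order, with columns headed "ABPM then HBPM, N = 302" and, for the reverse order, 301 participants. SAP Table 7, N = 547, ABPM minus HBPM: SBP -2.3 (95% CI -3.0 to -1.5); DBP -1.9 (-2.5 to -1.4). Differences below are HBPM minus ABPM.

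**Step 1. Difference within each order (Table 1 means).**

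| | ABPM first | HBPM first | Contrast |
|---|---|---|---|
| SBP | 105.7 - 104.7 = 1.0 | 106.9 - 103.4 = 3.5 | 2.5 |
| DBP | 61.8 - 60.4 = 1.4 | 62.9 - 60.1 = 2.8 | 1.4 |

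Each mean is rounded to 0.1, so each contrast is uncertain by up to 0.2 (SBP 2.3 to 2.7; DBP 1.2 to 1.6).

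**Step 2. Reproduce Table 7.** SBP: (1.0 + 3.5)/2 = 2.25, which agrees with 2.3. DBP: (1.4 + 2.8)/2 = 2.1 against 1.9. The DBP agreement is looser, which I attribute mostly to rounding and to Table 1 not being restricted to the 547 pairs.

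**Step 3. SD of the paired difference, from the Table 7 interval.** SD = half-width / t(0.975, 546) x sqrt(547).
- SBP: 0.75 / 1.964 = 0.382; x 23.39 = 8.93. Removing the order effect: sqrt(8.93² - 1.25²) = 8.84.
- DBP: 0.55 / 1.964 = 0.280; x 23.39 = 6.55. Removing the order effect: sqrt(6.55² - 0.7²) = 6.51.

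**Step 4. The D.11.5.1 test, read as a comparison of HBPM minus ABPM differences between orders.** The documents do not split the 547 by order; I assume 273/274. SE = SD x sqrt(1/273 + 1/274).
- SBP: SE = 0.756; t = 2.5/0.756 = 3.31; p about 0.001; 95% CI for the contrast 1.0 to 4.0. Varying the means and the Table 7 interval within rounding gives p from 0.0001 to 0.005. A 250/297 split barely changes it (t = 3.29).
- DBP: SE = 0.557; t = 1.4/0.557 = 2.51; p about 0.01. Over rounding, p runs from 0.002 to 0.05.

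Approximate 95% intervals by order for SBP are -0.05 to 2.05 (ABPM first) and 2.45 to 4.55 (HBPM first).

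**Step 5. What adjustment does to the headline.** The order-adjusted SBP difference is the unweighted mean of the two orders: 2.25, SE 0.756/2 = 0.378, 95% CI about 1.5 to 3.0. Unadjusted it is 2.3, SE 0.382, CI 1.5 to 3.0. The SE ratio is 0.99. If the share with ABPM first among complete pairs were 0.48 or 0.45, the unadjusted value would be 0.48 x 1.0 + 0.52 x 3.5 = 2.30, or 0.45 x 1.0 + 0.55 x 3.5 = 2.375, so plausible imbalance moves it very little.

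**The case against.** The strongest reply is that the result does not change. With orders at 302/301 a period effect cancels from the mean difference, and adjustment moves the SBP estimate by about 0.05 mm Hg and its SE by about 1%. This stands, and it rules out a stronger inference that a reader might draw, that Table 7 is biased or its conclusion wrong. It does not answer the mismatch between the documents or the unreported order contrast.

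Second, the trigger sentence is ambiguous. If it means mean sleep BP on each device compared between orders, Table 1 (taking n = 302/301) gives no significant result: ABPM SBP 104.7 v 103.4, p about 0.13; HBPM SBP 105.7 v 106.9, p about 0.21; ABPM DBP p about 0.62; HBPM DBP p about 0.10. In context, after a paired comparison of the devices, the reading as HBPM minus ABPM differences is more natural, but the wording does not settle it.

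Third, a reader might say that the SAP discards order altogether. It does not: Table 1 prints the order-specific means used here. The test, the adjustment and the difference by order are what is missing.

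Fourth, it is tempting to extend the point to Aim 1, where D.11.4.1 has a similar rule ("If the absolute differences between unattended and attended clinic BP and awake BP differs by randomization assignment, we will use a mixed model") and SAP item 2b names no terms ("using mixed model to determine the difference between the differences"). The documents show no comparable signal. Attended minus unattended SBP is 118.9 - 118.2 = 0.7 in one clinic order and 120.0 - 119.2 = 0.8 in the other; DBP is 0.7 and 0.4. These signed contrasts do not settle the rule on absolute differences, but they give no evidence of harm. Clinic order is also reversed at Visit 2 for every participant, and ABPM was never randomised in order against clinic BP, so the same terms could not separate method from period there.

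**Conclusion.** The point holds for Aim 2, as a gap between protocol and SAP and a reporting omission. On the natural reading of D.11.5.1 the trigger is clearly met for SBP (contrast about 2.5 mm Hg, p about 0.001) and probably for DBP (about 1.4, p about 0.01, reaching 0.05 at the edge of rounding), and Table 7 is unadjusted. The SBP contrast is about as large as the overall device difference of 2.3 mm Hg, and no SAP result reports it. The overall difference itself is essentially unbiased.

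The figures assume that Table 1 means for available participants approximate those of the 547 pairs, and that the pairs split about equally by order.

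A reader might call this a first-night effect of 2.5/2 = 1.25 mm Hg. That follows only if there is no carry-over and no device-by-order interaction, which two periods and two orders cannot separate from a period effect. A reader might also compare 1.0 and 3.5 with the 2.1 mm Hg in D.12.2.1, but that is a power figure and not a declared equivalence margin.

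**What to change.** 1. Delete the pre-test and the conditional clause in D.11.5.1.
2. Replace SAP item 5b with a device comparison that always includes period and randomised order, with site as the randomisation stratum; for example, a mixed model with device, period, order and site and a random participant effect. Period must be named: in a model of the device readings, assignment as a main effect alone does not remove a period effect from the within-person contrast.
3. Add to Table 7 the HBPM minus ABPM difference by order, with intervals, next to the overall difference.
4. State that this analysis was added after the tabulated results were available; it cannot be called prespecified. State also that the contrast between orders is twice a period effect only without carry-over or device-by-order interaction.

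No change to the Aim 1 Table 2 model is asked for on this ground.

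The cost is a wording change, one model and a few table cells. Order and site are already recorded, and no new data are needed.
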